#### Specific timepoints for assessments on days +1, +2, +3 and +4: - Cohorts 1-5

PK samples: +12h, +24h, +48h, +72h HAMD17: before start of infusion, +12h, +24h, +48h, +60h, +72h all done by CTNI CGI-I: +12h, +24h, +48h, +60h, +72h CGI-S: before start of infusion EPDS: before start of infusion, +60h STAI6: before start of infusion, +12h, +24h, +48h, +60h, +72h ECG: +12h, +24h, +48h, +72h Vital Signs: (BP/P/pO2/RR/Temp): before start of infusion, +4, +8h, +12, +18h, +24h, +32h, +40h, +48h, +56h, +60h, +72h SSS: before start of infusion, +8h, +32h, +56h, +72h CSSRS: before start of infusion, +12h, +36h, +60, +72h Safety laboratory tests and neurosteroid level: +48h Urinalysis drug and pregnancy test: +72h Physical examination: +72h AEs and concomitant medications are collected throughout the inpatient stay.

Q15min health checks are done from the time of admission to the time of discharge. Pulse oximetry (pO2) must be monitored throughout the infusion, including during the night when the subject is sleeping. The subject should be awakened if pulse oximetry falls < 91%.

The following priority order will be in effect when more than 1 assessment is required at a particular time point: 1) HAMD17 2) CGI-I/CGI-S 3) EPDS 4) STAI6 5) SSS 6) CSSRS 7) vital signs 8) ECG 9) safety labs and neurosteroid level 10) PK sample 11) neurosteroid level 12) urinalysis drug screen and pregnancy test 13) physical examination

Day 11 and Day 34 visits have visit windows of  $\pm$  3 and  $\pm$  5 days, respectively

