#### Table 1. Schedule of Assessments – Cohorts 1-5

Day	Day -14 to -1	Day 0	Day 1	Day 2	Day 3	Day 4	Day 11 (Day 7	Day 34 (Post
	-	-	(Start	-	(End	(Discharge)	Post Discharge)	Discharge
			Infusion in		Infusion			Day 30)
			AM, 0h)		in PM)			
VISIT	Screening	Admission	Infusion	Infusion	Infusion	Discharge	Follow-up	Follow-up
STAI6	Х		Х	Х	Х	Х	Х	Х
Q15 min health checks & pulse ox			throughout					

Specific timepoints for assessments on days +1, +2, +3 and +4: - Cohorts 1-5

PK samples: +12h, +24h, +48h, +72h HAMD17: before start of infusion, +12h, +24h, +48h, +60h, +72h all done by CTNI CGI-I: +12h, +24h, +48h, +60h, +72h CGI-S: before start of infusion EPDS: before start of infusion, +60h STAI6: before start of infusion, +12h, +24h, +48h, +60h, +72h ECG: +12h, +24h, +48h, +72h Vital Signs: (BP/P/p02/RR/Temp): before start of infusion, +4, +8h, +12, +18h, +24h, +32h, +40h, +48h, +56h, +60h, +72h SSS: before start of infusion, +8h, +32h, +56h, +72h CSSRS: before start of infusion, +12h, +36h, +60, +72h Safety laboratory tests and neurosteroid level: +48h Urinalysis drug and pregnancy test: +72h Physical examination: +72h AEs and concomitant medications are collected throughout the inpatient stay.

Q15min health checks are done from the time of admission to the time of discharge. Pulse oximetry (pO2) must be monitored throughout the infusion, including during the night when the subject is sleeping. The subject should be awakened if pulse oximetry falls < 91%.

The following priority order will be in effect when more than 1 assessment is required at a particular time point: 1) HAMD17 2) CGI-I/CGI-S 3) EPDS 4) STAI6 5) SSS 6) CSSRS 7) vital signs 8) ECG 9) safety labs and neurosteroid level 10) PK sample 11) neurosteroid level 12) urinalysis drug screen and pregnancy test 13) physical examination

Day 11 and Day 34 visits have visit windows of ± 3 and ± 5 days, respectively

#### Table 2. Schedule of Assessments - Cohort 6

Day	Day -14 to -1	Day 0 Admission	Day 1	Day 1°	Day 2f	Days 3 & 5	Day 4	Day 8	Days 10 & 13	Day 11	Day 15	Day 22	Day 29	Day 36	Day 57	Day 71
VISIT	Screenin g		Baseline	Post-BL	Discharge & Outpatient	Safety call	V3 HAMD Call	V4 outpt	Safety call	V5 HAMD Call	V6 outpt	V7 outpt	V8 outpt	l st Follow- up	2 nd Follow- up	3rd Follow- up
Informed consent	X															
Demographics, Medical History	X		33								23 - 23 					
MINI neuropsychiatric interview	X															
Inclusion/Exclusion criteria	X	X														

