### 8.2 Other Definitions

#### +72h

72 hours after start of infusion (0hr) based on visit window. If a subject is discontinued from the study during the inpatient treatment phase (Day 1 through Day 4), all assessments scheduled at +72h will be collected at the time of study exit, but the assessments will be allocated to analysis visits based on visit windows detailed in Section 8.4.

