### 8.4 Analysis Time Point/Visit Windows

For data summarized on a per time point or per visit basis, the windows used for analyses are defined below unless stated otherwise.

Protocol Visit	Window Description (Target Day/Time Point)	Protocol Window (with respect to Visit Day as defined in the protocol)	Analysis Window (with respect to Study Day and Study Time in minutes as defined in this SAP)
Screening	Screening	Day -14 to -1	Study Day < -1
Day 0	Day 0 (Admission)	Day 0	Study Day = -1
Day +1	Day 1 (Pre-Infusion)	N/A	Study Day = 1 and Study Time < 0
Day +1	Day 1 (+4h)	N/A	0 <= Study Time < 360
Day +1	Day 1 (+8h)	N/A	360 <= Study Time < 600
Day +1	Day 1 (+12h)	N/A	600 <= Study Time < 900
Day +1	Day 1 (+18h)	N/A	900 <= Study Time < 1260
Day +2	Day 2 (+24h)	N/A	1260 <= Study Time < 1680
Day +2	Day 2 (+32h)	N/A	1680 <= Study Time < 2160
Day +2	Day 2 (+40h)	N/A	2160 min <= Study Time < 2640 min
Day +3	Day 3 (+48h)	N/A	2640 min <= Study Time < 3120 min
Day +3	Day 3 (+56h)	N/A	3120 min <= Study Time < 3480 min
Day +3	Day 3 (+60h)	N/A	3480 min <= Study Time < 3960 min
Day +4	Day 4 (+72h)	N/A	3960 min <= Study Time < 2 days after 72 hr timepoint

For the IV only cohorts (cohorts 1-5), the following analysis time points and visit windows will be used.

PRS 005 T 17 F

Strictly Confidential. © 2004-2015, PRA Health Sciences. All rights reserved.

Page 16 of 35

Protocol Visit	Window Description (Target Day/Time Point)	Protocol Window (with respect to Visit Day as defined in the protocol)	Analysis Window (with respect to Study Day and Study Time in minutes as defined in this SAP)
Day 11	Day 11	Day 8 to 14	5 <= Study Day < 23
Day 34	Day 34	Day 29 to Day 39	23 < Study Day < 45

For the IV to oral cohort (cohort 6), the following analysis time points and visit windows will be used.

Protocol Visit	Window Description (Target Day/Time Point)	Protocol Window (with respect to Visit Day as defined in the protocol)	Analysis Window (with respect to Study Day and Study Time in minutes as defined in this SAP)
Screening	Screening	Day -14 to -1	Study Day < -1
Day 0	Day 0 (Admission)	Day 0	Study Day = -1
Day +1	Day 1 (Pre- Infusion)	N/A	Study Day = 1 and Study Time < 0
Day +1	Day 1 (Post- Infusion)	N/A	Study Day = 1 and Study Time >= 0
Day 2	Day 2 (Discharge)	N/A	Study Day = 2
Day 4	Day 4 (HAMD Call)	Day 3 to 5	3 <= Study Day <= 5 for HAMD only
Day 8	Day 8	Day 6 to 10	6 <= Study Day <= 9 for HAMD, 3 <= Study Day <= 11 otherwise

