Day 11	Day 11 (HAMD Call)	Day 10 to 12	10 <= Study Day <= 12 for HAMD only
Day 15	Day 15	Day 12 to 18	13 <= Study Day <=18 for HAMD, 12 <= Study Day <= 18 otherwise
Day 22	Day 22	Day 19 to 25	19 <= Study Day <= 25
Day 29	Day 29	Day 26 to 32	26 <= Study Day <= 32
Day 36	Day 36	Day 33 to 39	33 <= Study Day <= 46
Day 57	Day 57	Day 54 to 60	47 <= Study Day <= 64
Day 71	Day 71	Day 68 to 74	65 <= Study Day <= 77

The analysis windows are aligned with, but wider than, those specified by the schedule of visits and procedures in the protocol in order to include in analyses of all study data (including unscheduled visit data) that fall outside of protocol visit windows. If multiple data points are observed within a single analysis window, the latest observation will be used for analysis.

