### 12.5 Efficacy Analyses

Statistical analysis of efficacy endpoints will primarily be done using the mITT set and will be done only to aid in interpretation as the trial was not powered for inferential hypothesis testing. As such, there will be no adjustments for inflation of type 1 error due to multiplicity.

For efficacy endpoints expressed as continuous variables, summary tables will show continuous summary statistics for each time point of data collection (visit) as well as least squares (LS) means with standard errors (SEs) and associated p-values from mixed model repeated measures (MMRM) analysis. Summary statistics by time point will also be displayed graphically using bar and/or line charts. MMRM models will include fixed effects for treatment, visit, and the treatment-by-visit interaction, and the baseline observation will be included as a covariate. Repeated measurements are made on each subject. Residuals will be evaluated for substantial departure from normality and independent and constant variance. Methods such as data transformation, detecting and assessing the influence of outliers, and alternative analytical approaches (e.g., non-parametric) may be used to address assumption deviations. An unstructured covariance will be the default covariance structure but other structures (e.g., compound symmetry) may be used to evaluate sensitivity to the choice of structure or, if necessary, to achieve convergence. MMRM assumes missing observations are missing at random (MAR); i.e., missingness depends only on variables other than the outcome that are available in the database. Because the MAR assumption is not testable, and because it seems possible that subjects with poorer outcome may be more likely to miss trial assessments, a sensitivity analysis may be done in which all missing data will be imputed. Conservatively, multiple imputation with a pattern-mixture model will be used; specifically, for all subjects with missing observations regardless of treatment assignment, imputation will be based only on subjects randomized to placebo. The imputation method will be fully conditional specification (FCS) regression with 25 imputations. Variables in the imputer's model will be observed values at each time point included in the MMRM analysis, including baseline.

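### In Cohorts 1-5 the SAP windows HAMD17 on the vital-signs grid, so a rating at 52 to <58 h cannot be the primary +60h value

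*SAP*

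**What the plan says.** SAP 8.4 sets the scope of its tables: "For data summarized on a per time point or per visit basis, the windows used for analyses are defined below unless stated otherwise". For Cohorts 1-5 there is a single set of eleven post-dose inpatient rows, from +4h to +72h. The +56h row is "3120 min <= Study Time < 3480 min" and the +60h row is "3480 min <= Study Time < 3960 min". The protocol-window column reads N/A for all of them, so no tolerance is stated elsewhere.

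The notes to Protocol Table 1 schedule vital signs at "before start of infusion, +4, +8h, +12, +18h, +24h, +32h, +40h, +48h, +56h, +60h, +72h". The notes to SAP Table 1 give "HAMD17: before start of infusion, +12h, +24h, +48h, +60h, +72h all done by CTNI". CGI-I and STAI6 share those five post-dose times. EPDS has one post-dose inpatient time, +60h.

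The Cohort 6 table in SAP 8.4 has separate HAMD limits on its Day 4, 8, 11 and 15 rows. The Cohorts 1-5 table has none.

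For women who leave during the inpatient phase, SAP 8.2 collects the +72h battery at exit, but "the assessments will be allocated to analysis visits based on visit windows detailed in Section 8.4". SAP 8.4 adds that "The analysis windows are aligned with, but wider than, those specified by the schedule of visits and procedures in the protocol", in order to keep unscheduled data in the analyses, and that the latest observation in a window is used. SAP 12.5 states: "MMRM models will include fixed effects for treatment, visit, and the treatment-by-visit interaction", with an unstructured covariance by default. It does not list the visits. SAP 12.5.1 makes HAMD17 change to 60 h (on Day 3) the primary endpoint for these cohorts.

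**The concern.** A window table should send a slightly early or late assessment to the scheduled visit it was meant for. Here the row before +60h exists only because vital signs are taken at +56h. A HAMD17 done at 57.5 h, while the infusion is still running, is labelled +56h, and that woman then has no +60h score. One done at 65.5 h, more than 5 h after the infusion ended, counts as +60h. The same applies to CGI-I, STAI6 and EPDS.

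Exit ratings have a related problem. A HAMD17 at an exit at 32 h becomes a +32h visit that no other woman is scheduled to have. If such rows enter the MMRM, they add a sparse visit level with a possibly empty cell in the other arm. If they are left out, data are set aside despite the stated aim of keeping them. The SAP does not say which, so the choice could be made after the data are seen.

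**Working it through.** **1. Reproduce the grid.** Take midpoints of adjacent vital-signs times (4, 8, 12, 18, 24, 32, 40, 48, 56, 60, 72 h) and multiply by 60. For example, (56 + 60)/2 = 58 h = 3480 min and (60 + 72)/2 = 66 h = 3960 min. The full set is 360, 600, 900, 1260, 1680, 2160, 2640, 3120, 3480 and 3960 min. All ten internal limits in SAP 8.4 match, so the table is the vital-signs grid.

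**2. Mark the rows by the HAMD17 schedule.**

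| Row | Hours | HAMD17 scheduled |
|---|---|---|
| +4h | 0-6 | no |
| +8h | 6-10 | no |
| +12h | 10-15 | yes |
| +18h | 15-21 | no |
| +24h | 21-28 | yes |
| +32h | 28-36 | no |
| +40h | 36-44 | no |
| +48h | 44-52 | yes |
| +56h | 52-58 | no |
| +60h | 58-66 | yes |
| +72h | 66-120 | yes |

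Rows without a scheduled HAMD17: 6 + 4 + 6 + 8 + 8 + 6 = 38 h. That is 38/60 = 63% of the infusion period, or 38/66 = 58% of the time before the +72h row opens.

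**3. Tolerance at +60h.** Early side: 60 - 58 = 2 h. Late side: 66 - 60 = 6 h (exclusive). A rating more than 2 h and up to 8 h early (52 to <58 h) goes to +56h. One more than 8 h and up to 16 h early (44 to <52 h) goes to +48h, where the latest-observation rule lets it replace the on-time +48h score.

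**4. Illustrative frequency.** The documents give no rating times. Assume they are normal around 60 h with standard deviation s. The share in the +56h row is Φ((58 - 60)/s) - Φ((52 - 60)/s). With a +60h window opening at 54 h, the share falling before it is Φ((54 - 60)/s).

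| s (assumed) | In +56h row now | Before 54 h |
|---|---|---|
| 1 h | 2.3% | 0.0% |
| 2 h | 15.9% | 0.1% |
| 3 h | 24.9% | 2.3% |

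**5. Windows from the HAMD17 schedule.** Midpoints of 12, 24, 48, 60 and 72 h are 18, 36, 54 and 66 h. The +60h window becomes 54 to <66 h (3240 to <3960 min), 6 h on each side.

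**6. Effect on the 38 h.** With no lower limit for +12h, a rating at 0-10, 18-21, 36-44 or 54-58 h would fill a scheduled row that a woman leaving then would otherwise lack: 10 + 3 + 8 + 4 = 25 h. The other 13 h (15-18, 28-36 and 52-54 h: 3 + 8 + 2) fall in a row whose scheduled time has already passed. Under the latest-observation rule, a rating there would overwrite the on-time score. New cuts alone are therefore not enough, and the tie rule must change too.

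**7. Overlap.** The +72h row ends at 72 + 48 = 120 h. Day 11 opens on Study Day 5. For a 10:00 start (assumed; the protocol says morning), Study Day 5 begins at 14 + 72 = 86 h, so the rows overlap for 120 - 86 = 34 h. The tie rule works only within one window.

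**The case against.** The strongest reply is that nothing is shown to be lost. A reader might infer that an early or exit rating disappears from the primary analysis. The documents do not say that: SAP 12.5 names no MMRM visits, SAP 8.4 aims to include unscheduled data, and a woman with any post-randomization efficacy assessment stays in mITT. If the +56h row enters the model, the score still informs +60h through the covariance. This stands. What remains is that the rating cannot be the +60h value and that its handling is unstated.

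Other stronger readings also fail:

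- Not every rating more than 2 h early is affected. Beyond 8 h early it falls in +48h, where HAMD17 is scheduled.
- Not every exit is affected. Exits at 10-15, 21-28, 44-52 h and from 58 h land in scheduled rows. An exit score at 32 h should not count as +60h under any sensible rule.
- The 63% is a share of hours. It would be a share of exits only if exits were uniform over the infusion, and nothing supports that. Protocol 1.2.1.4 reports no adverse events leading to discontinuation in Cohorts 1 and 2 or in the 13 Cohort 3 subjects reviewed.
- One missing +60h value is 10% of an arm in a 20-subject cohort (1 of 10), but the MMRM keeps that woman's other visits.
- Nothing in the documents shows that ratings moved by scheduling relate to outcome.
- Model failure does not follow. SAP 12.5 allows other covariance structures if needed for convergence.

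In addition, subjects are inpatients and HAMD17 comes first in the assessment order, which should limit timing error. The +72h overlap has little practical reach, since discharge is at 72 h and the protocol's Day 11 window is Days 8 to 14.

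**Conclusion.** The point holds in limited form. Followed as written, SAP 8.4 assigns a HAMD17 at 52 to <58 h to a time point with no scheduled HAMD17 and excludes it as the +60h value, while accepting one nearly 6 h late. This is the result of a stated rule and not merely a missing detail. Exit ratings in 38 of the 60 infusion hours become time points scheduled for no one, and their place in the MMRM is unspecified. The overlap of +72h with Day 11 is a separate drafting error.

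The window limits are exact. The frequency is unknown, and the 2.3% to 24.9% range rests wholly on the assumed spread of rating times. Efficacy is unpowered and hypothesis-generating, so no error rate or power figure is affected. The change is still worth making because SAP 12.5.1 gives the mean difference on this endpoint the most weight in judging efficacy, the cohorts are small, and the SAP already writes HAMD-specific windows for Cohort 6.

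**What to change.** Keep the present grid for vital signs. For the efficacy scales in Cohorts 1-5:

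- **HAMD17, CGI-I, STAI6:** cut at 18, 36, 54 and 66 h, so that +60h is 54 to <66 h. Give +12h a sensible lower limit (6 h, for example, would make it symmetric), so that a rating minutes after the start of dosing is not called +12h.
- **+72h row:** end it at Study Day 4, which removes the overlap with Day 11.
- **Tie rule:** for these variables, use the observation closest to the target time in place of the latest, so that an exit or stray rating does not overwrite an on-time score.
- **EPDS:** set a bounded +60h window, for example 54 to <66 h. Midpoints would open it at 0 h, because +60h is its only post-dose inpatient time.
- **MMRM:** name the visits as the scheduled HAMD17 times, and list actual rating times for +60h.

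The cost is one SAP table and reprogrammed visit allocation. SAP 3.0 allows amendment up to unblinding, so this should be signed off before the lock for the Cohorts 1-3 analysis in SAP 10.2.

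There are two downsides. A +60h value may come from up to 6 h before the end of infusion, which the listing of times would show. An off-time rating that shares a window with an on-time one is listed only.

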### 7.3.2 **During Infusion (Days +1 to +4)**

- Start bolus/infusion in the morning of Day +1 (0h) after baseline assessments are completed
- CTNI to conduct interviews for HAMD17 (+12h, +24h, +48h, +60h, +72h)
- Conduct interviews for CGI-I (+12h, +24h, +48h, +60h, +72h)
- EPDS (+60h)
- STAI6 (+12h, +24h, +48h, +60h, +72h)
- Collect AEs
- Collect ECG (+12h, +24h, +48h, +72h)
- Collect VS (BP, pulse, respiratory rate, pulse oximetry, temperature): (+4, +8h, +12, +18h, +24h, +32h, +40h, +48h, +56h, +60h, +72h)
- Collect SSS (+8h, +32h, +56h, +72h)
- Collect pharmacokinetic samples (+12h, +24h, +48h, +72h)
- Record concomitant medications
- Lower the infusion rate to half what was prescribed for the cohort (for example, lower the infusion rate from 4 mg/h to 2 mg/h) (+48h)
- Collect safety laboratory tests (+48h)
- Collect neurosteroid level (+48h)
- End infusion (+60h)
- Collect urine sample for urinalysis, drug screen and urine pregnancy test (+72h)
- Conduct CSSRS interview (+12h, +36h, +60h, +72h)
- Perform a physical examination (+72h)

- Stop monitoring of pulse oximetry and Q15 min health checks (+72h)
- Discharge subject (+72h)

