Start 3-day taper		i la contra c										64	x			.

a Infusion starts at 9 am and ends 6 hours later at 3 pm and is administered at a constant rate of 40 mL/hr.

b Twelve pharmacokinetic samples are collected in Cohort 6:

On Day 1 subjects will have 6 PK samplings: at 1 hour after the end of the 6-hour infusion (i.e., at 4 pm), at 7 pm (just prior to the oral dosing), and at 1, 2, 3, and 4 hours post oral dosing (at 8, 9, 10, and 11 pm) as well at 8 am the following morning (on Day 2) prior to discharge.

A pharmacokinetic sample is also collected on Days 8, 15, 22, 29, and 36 during the study visit.

c All HAMD17 ratings, except the one done at screening, will be conducted by CTNI raters.

 $^{d}$ Q15min health checks are done from the time of start of the infusion to the time of discharge. Pulse oximetry (pO2) must be monitored from the start of the infusion throughout the inpatient period, including during the night when the subject is sleeping. The subject should be awakened if pulse oximetry falls < 91%.

e On Day +1 all efficacy assessments should be conducted first before lab draws, if possible.

f All Day +2 assessments, including PK and neurosteroid levels, are to be done before the subject is discharged from the unit.

The following priority order will be in effect when more than 1 assessment is required at a particular time point: 1) HAMD17 2) CGI-I/CGI-S 3) EPDS 4) STAI6 5) SSS 6) CSSRS 7) vital signs 8) ECG 9) safety labs and neurosteroid level 10) PK sample 11) neurosteroid level 12) urinalysis drug screen and pregnancy test 13) physical examination

All outpatient visits have  $a \pm 3$ -day visit window, except Visits 3 and 5 which have just  $a \pm 1$ -day visit window and Visits 4 and 6 which have  $a \pm 2$ -day visit window.

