#### Study day

Study day is defined relative to the date of the first dose of study drug. For assessments that occur after this visit date, study day is calculated as (assessment date – study drug first dose date + 1). For assessments that occur prior to study drug first dose date, study day will be calculated as (assessment date – study drug first dose date); there is no Study Day 0.

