#### Study time

Study time (in minutes) is defined relative to the time of the first dose of study drug (0 hour on the morning of Day 1).

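### In Cohorts 1-5 the SAP's +72h and Day 11 analysis windows overlap by about 24 to 36 hours, and no rule assigns a record that meets both

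*SAP*

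**What the plan says.** The table in SAP 8.4 for the IV-only cohorts gives the Day 4 (+72h) row the analysis window "3960 min <= Study Time < 2 days after 72 hr timepoint". The next row, Day 11, has "5 <= Study Day < 23". The two rows use different clocks. Under SAP 8.2, Study Time counts minutes from the first dose, while Study Day counts calendar dates, with the first-dose date as Day 1.

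Below the tables the SAP adds: "If multiple data points are observed within a single analysis window, the latest observation will be used for analysis". It explains that the analysis windows are wider than the protocol windows "in order to include in analyses of all study data (including unscheduled visit data) that fall outside of protocol visit windows". It does not say what to do with one record that satisfies two windows.

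In the Protocol (7.3.2, 7.4.1 and the notes to Table 1), the +72h assessments are the discharge assessments on Day 4. The next visit is Day 11 with a window of 3 days either side, so Day 8 at the earliest.

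**The concern.** A visit-window table should send each record to one row. Here everything recorded on Study Day 5 meets the definition of both +72h and Day 11, and on an elapsed-time reading so does the first part of Day 6. A programmer must then either use such a record twice or make up a rule that the SAP does not contain.

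The +72h row shows status 12 h after the infusion ends. HAMD17, CGI-I, STAI6, vital signs, C-SSRS and the urine tests are scheduled at both +72h and Day 11, so they can be affected in both rows. ECG and SSS are scheduled at +72h but not at Day 11, so for them only the discharge row is at risk.

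**Working it through.** **Inputs**
- +72h row: lower limit 3960 min; upper limit 2 days after the 72 h time point (SAP 8.4).
- Day 11 row: Study Days 5 to 22 (SAP 8.4).
- Study Time runs from first dose; Study Day is calendar-based (SAP 8.2).
- Clock hour of infusion start, *s*: Protocol 7.3.2 says "Start bolus/infusion in the morning of Day +1 (0h) after baseline assessments are completed" and gives no clock time for Cohorts 1-5. The only stated clock time is in the footnote to Protocol Table 2 for Cohort 6: "Infusion starts at 9 am and ends 6 hours later at 3 pm". Using 09:00 for Cohorts 1-5 is therefore an assumption, and I take 06:00 to 12:00 as the range.

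**Step 1. Limits of the +72h row.** 3960 / 60 = 66 h. 72 + 48 = 120 h (7200 min). Length: 120 - 66 = 54 h.

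**Step 2. Start of Study Day 5.** Midnight at the end of Day 4 is 4 x 24 - *s* = 96 - *s* hours after first dose.

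**Step 3. Overlap.** 120 - (96 - *s*) = 24 + *s* hours.

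| Start | Day 5 begins | +72h row ends | Overlap | Share of 54 h |
|---|---|---|---|---|
| 06:00 | 90 h | Day 6, 06:00 | 30 h | 56% |
| 09:00 | 87 h | Day 6, 09:00 | 33 h | 61% |
| 12:00 | 84 h | Day 6, 12:00 | 36 h | 67% |

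**Step 4. Other reading.** If the 2 days are calendar days, the row stops before Day 4 + 2 = Day 6. The overlap is then all of Day 5, which is 24 h. The rows overlap on either reading.

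**Step 5. The other boundaries.** The ten boundaries between inpatient time points are exact midpoints of adjacent targets. For example, (56 + 60) / 2 = 58 h = 3480 min, and (60 + 72) / 2 = 66 h = 3960 min. The Day 11/Day 34 boundary is (11 + 34) / 2 = 22.5, rounded to 23. All of these are exclusive, and the Cohort 6 windows do not overlap either. Only the +72h/Day 11 boundary mixes elapsed time with calendar day.

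**Step 6. Applying the rules as written.**
- *No value on Day 5 or early Day 6:* no effect.
- *Unscheduled Day 5 value, Day 11 visit attended:* the Day 5 value is the latest in the +72h row and displaces the discharge value there. The Day 11 row takes the later visit. This comes from the 120 h limit and the latest-value rule. It would remain if Day 11 opened exactly at 120 h.
- *Unscheduled Day 5 value, nothing later through Day 22:* the value displaces the discharge value at +72h and the same record also qualifies for Day 11. The second part comes from the overlap.

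**Step 7. Size if it happens.** SAP 6.1 plans about 10 to 30 women per cohort, randomized 1:1, so about 5 to 15 per arm. One affected record is 1/15 = 7% to 1/5 = 20% of an arm at that visit.

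**Step 8. Primary endpoint.** The +60h row runs from 3480 min to below 3960 min and is not involved.

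**The case against.** The strongest answer is that the overlap is nearly empty in practice. Nothing is scheduled between discharge and Day 8. All HAMD17 ratings after screening are made by the central raters (Protocol 7.8.6.2), and no extra rating is planned in the gap. Early-exit assessments do not fill it: SAP 8.2 sends +72h assessments to study exit only for women who discontinue between Day 1 and Day 4. The SAP also states openly that it widened the windows to take in unscheduled data, so a long +72h row is partly a deliberate choice. All of this stands, and it limits how often the problem can arise. It does not supply the missing rule for a record in two windows.

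A reader might infer three stronger things that the documents do not support.
- *That discharge values will be replaced as a matter of course.* Replacement needs an unscheduled or late value on Day 5 or early Day 6.
- *That one rating will certainly enter the repeated-measures model as two visits.* The SAP is silent on records that meet two rows; it does not say they are used twice. Double use also needs no later value through Day 22.
- *That the substituted values will be worse because extra visits are prompted by problems.* No passage says so. Protocol 8.1.5 calls for follow-up of abnormal laboratory, vital-sign and ECG values found at the end of treatment until they return to range, and Protocol 7.8.5.2 allows abnormal laboratory values to be repeated. A normalised repeat of a vital sign, ECG or urinalysis could replace an abnormal discharge value, which is the opposite direction.

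**Conclusion.** The two rows are wrong as written because they are not mutually exclusive. The overlap is about 30 to 36 h on the elapsed-time reading with a start between 06:00 and 12:00, and 24 h on the calendar-day reading. The 33 h figure holds only for a 09:00 start, which the documents state for Cohort 6 alone.

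The practical weight is small. Affected records are probably few, and the 7 to 20% share of an arm applies only if one exists. Any effect falls on secondary time points and safety summaries, in a plan whose efficacy analyses are described as hypothesis-generating (SAP 12.0). It would be wrong to infer that the primary result is at risk. The point is worth correcting because the rule misallocates data whenever it applies and the correction is simple.

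**What to change.** In the SAP 8.4 table for Cohorts 1-5, change the +72h row to: 3960 min <= Study Time and Study Day <= 4. Leave the Day 11 row as it is. The overlap becomes 0 h, and a post-discharge value can no longer displace the discharge assessment. The 72 h target keeps a margin of 12 h (noon start: 84 - 72) to 18 h (06:00 start: 90 - 72) before the row closes.

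An alternative is to open Day 11 where the +72h row ends. That also stops one record qualifying twice, but it leaves Day 5 and early Day 6 values able to replace the discharge value.

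The cost is one table cell, the matching line of code, and an SAP amendment that the sponsor signs before programming changes (SAP 3.0). SAP 3.0 allows amendment only up to unblinding and SAP 10.2 plans an unblinded analysis after Cohort 3, so the change should precede that analysis. One consequence must be accepted: a discharge assessment delayed to Day 5 would move to the Day 11 row.
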